5.2. Participant Disposition

The number of participants in the following disposition categories through M-44 will be summarized by treatment group and overall based on the Full Analysis Set (including both randomized and nonrandomized participants), the All Treated Analysis Set, and the Dose Adjustment Analysis Set:

- Participants who received study intervention
- Participants who discontinued study intervention
 - Reasons for discontinuation of study intervention (including COVID-19 and the regional crisis)
- Participants who terminated study prematurely
 - Reasons for termination of study (including COVID-19 and the regional crisis)

Listings of participants based on the **All Treated Analysis Set** will be provided for the following categories:

- Participants who discontinued study intervention
- Participants who terminated study prematurely

In addition, the number and percentage of participants who have a dose adjustment over time will be summarized for participants in the **Randomized Full Analysis Set**.

5.3. Primary Endpoint Analysis

The primary endpoint is clinical remission at Week M-44.

5.3.1. Definition of Endpoint

Clinical remission based on modified Mayo score components: A Mayo stool frequency subscore of 0 or 1, a Mayo rectal bleeding subscore of 0, and a Mayo endoscopy subscore of 0 or 1 with no friability present on the endoscopy, where the stool frequency subscore has not increased from induction baseline.

5.3.1.1. Mayo Score, Partial Mayo Score, and Modified Mayo Score

The Mayo score (Protocol Section 8.1.1.) was developed from the criteria of Truelove and Witts¹ for mild, moderate, and severe UC and from the criteria of Baron et al² for grading endoscopic appearance.

The Mayo score consists of the following 4 subscores:

- Stool frequency
- Rectal bleeding
- Findings of endoscopy
- Physician's global assessment (PGA)

Each subscore is rated on a scale from 0 to 3, indicating normal to severe activity, as defined in Attachment 1.

The full **Mayo score** is calculated as the sum of 4 subscores (stool frequency, rectal bleeding, PGA, and endoscopy findings) and ranges from 0 to 12 points. A score of 3 to 5 points indicates mildly active disease, a score of 6 to 10 points indicates moderately active disease, and a score of 11 to 12 points indicates severely active disease.

The **partial Mayo score**, which is the Mayo score without taking into account the findings of endoscopy, is calculated as the sum of stool frequency, rectal bleeding, and PGA subscores, and may take on values from 0 to 9.

The **modified Mayo score**, which is the Mayo score without the PGA subscore, is calculated as the sum of the stool frequency, rectal bleeding, and endoscopy subscores, and may take on values from 0 to 9.

Due to the requirement for endoscopy findings for the evaluation of the Mayo score, it is not feasible to evaluate the Mayo score at each scheduled visit in the study. Therefore, the Mayo score will be evaluated at Week M-44 and at the time when loss of clinical response needs to be confirmed following a clinical flare, and the partial Mayo score will be evaluated at the other study visits. Note that the modified Mayo score is not a separate evaluation from the Mayo score as the latter contains all the components that are needed for the calculation of the modified Mayo score.

Mayo Stool Frequency and Rectal Bleeding Subscores

The eCRF captures seven days of rectal bleeding data and the number of stools per day prior to each visit at which the Mayo score or partial Mayo score is collected. Data from 3 of these 7 days are used to calculate the Mayo stool frequency and rectal bleeding subscores; sites are instructed to check the boxes next to the 3 days which are used (see below for information on what days the sites are instructed to use).

The Mayo rectal bleeding subscore is calculated using the average rectal bleeding number for the three days based on the criteria in Attachment 1.

The Mayo stool frequency subscore is calculated as follows: the absolute stool number is the average of the daily stool number over the three days; at the screening visit, each person indicates the number of stools he/she passed in a 24-hour period when in remission or before his/her UC diagnosis; the stool frequency subscore will be calculated based on the criteria in Attachment 1 by subtracting the number of stools when in remission or prior to UC from the absolute stool number.

Instructions on which 3 days to use in the calculation of the Mayo rectal bleeding and stool frequency subscores: Sites are directed to use the most recent 3 consecutive days within the 7 days prior to the visit and are directed to exclude the following:

- The day medications were taken for constipation, diarrhea or irregularity
- The day(s) of a procedure or preparation for procedure (e.g., enema, other laxatives, or clear liquid diet) that would affect stool frequency and/or blood content of the stool
- The 48 hours after the use of antimotility agents (i.e., diphenoxylate hydrochloride with atropine sulfate, loperamide or other opioids)

Note: For participants maintained on a chronic stable dose of antimotility agents throughout the study, the days on which these agents are taken will not be excluded from consideration in calculating the Mayo score

• The 48 hours immediately following a colonoscopy

If three consecutive days are not available, the sites are instructed to choose two consecutive days and the closest nonconsecutive day. If two consecutive days are not available, then three nonconsecutive days closest to the visit should be chosen. If 3 days (within the 7 days prior to the indicated visit) that meet the criteria defined above are not available, then the absolute stool number, stool frequency subscore and rectal bleeding subscore cannot be calculated and will be missing in the eCRF.

Mayo Endoscopy Subscore

The endoscopic findings will be based on the criteria of the Mayo endoscopy subscore described in Attachment 1. The endoscopic findings will be assessed by the investigator (i.e., local endoscopist) during the endoscopy procedure and by a central reader reviewing a video of the endoscopy. The endoscopy may be either a colonoscopy or sigmoidoscopy. A full colonoscopy will replace a sigmoidoscopy if screening for polyps or dysplasia is required. The central reader will also perform a friability assessment (Yes/No) for each endoscopy.

Participant eligibility at baseline will be based on the final reported endoscopic subscore as determined by the following process:

- If the local endoscopist and the central reader agree on the endoscopic subscore, the agreed score will be the final reported endoscopic subscore.
- If there is a discrepancy between the local endoscopist and the central reader subscores, the video endoscopy will be submitted to a second central reader (designated for adjudication), who is blinded to the scores of the local and the first central reader. The median score of the 3 completed reads (i.e., local read, central read 1, and central read 2 designated for adjudication) will be the final reported endoscopic subscore.

Further details are provided in the Imaging Charter.

Unless otherwise specified, the analysis of endpoints that include the Mayo endoscopy subscore will be based on the final reported endoscopic subscore. If the final reported endoscopic subscore is not available, the corresponding central endoscopy score (central read #1) will be used, if available. If the central endoscopy score (central read #1) is also missing, then the

local endoscopy score will be used, if available. If the local endoscopy score is also not available, then the endoscopy subscore for the analysis will be left missing.

Mayo Physician's Global Assessment Subscore (PGA)

The PGA acknowledges the 3 other Mayo subscores, the patient's recall of abdominal discomfort and general sense of well-being, and other observations, such as physical findings and the patient's performance status.

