8.1.1. Mayo Score

The **Mayo score** (see Appendix 10 [Section 10.10]) was developed from the criteria of Truelove and Witts (Truelove 1955) for mild, moderate, and severe UC and from the criteria of Baron et al (Baron 1964) for grading endoscopic appearance. The Mayo score is calculated as the sum of 4 subscores (stool frequency, rectal bleeding, physician's global assessment, and endoscopy findings) and ranges from 0 to 12 points. The **partial Mayo score** is the Mayo score without the endoscopy subscore and ranges from 0 to 9 points. The **modified Mayo score** is the Mayo score without the physician's global assessment and ranges from 0 to 9 points. **Mayo scores** are calculated using the following:

1. The stool frequency and rectal bleeding data from the most recent consecutive 3-day period within the 1 week before the visit. The average of the 3-day period will be used to calculate the stool frequency and rectal bleeding scores for the visit. Days on which the following conditions are met should be excluded from the calculation:
 - a. The day on which medications for constipation, diarrhea, or irregularity were taken. (For participants maintained on a stable dose of bulking or stool-softening agents throughout the study, the days on which these agents are taken should not be excluded from consideration in calculating the Mayo score.)
 - b. The day(s) of a procedure or preparation for a procedure (eg, enemas, other laxatives, a clear liquid diet) that would affect bowel frequency and/or blood content of the stool.
 - c. The 48 hours after the use of antimotility agents (ie, diphenoxylate hydrochloride with atropine sulfate, loperamide, or other opioids).

Note: For participants maintained on a chronic stable dose of antimotility agents throughout the study, the days on which these agents are taken should not be excluded from consideration in calculating the Mayo score.
 - d. The 48 hours immediately following a colonoscopy.
2. The physician's global assessment.
3. The results of a sigmoidoscopy or colonoscopy.

The endoscopic findings will be assessed by the investigator (ie, local endoscopist) during the endoscopy procedure and by the central reader reviewing a video of the endoscopy. Participant eligibility at baseline will be based on the final reported endoscopic subscore as determined by the following process:

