5.3.2.3. Supplementary Estimands for the Primary Endpoint

Estimand 2 (Composite Strategy for all ICEs):

The attributes of this supplementary estimand are the same as those for the primary estimand with the exception of the Variable (Endpoint) and the strategies for the intercurrent events, which are described as follows:

Variable (Endpoint): Clinical remission at Week M-44, where participants are considered to have achieved clinical remission if they fulfill the clinical remission criteria based on modified Mayo score components (Section 5.3.1.). Participants who have intercurrent events in categories 1-6 prior to the Week M-44 visit will be considered to not have achieved clinical remission at Week M-44.

Intercurrent Events and corresponding strategies:

For this estimand, the intercurrent events (given below) are addressed with a Composite Strategy.

- 1. An ostomy or colectomy (partial or total)
- 2. Have a dose adjustment (including a sham dose adjustment; Section 1.3.1.)
- 3. Prohibited change in UC medication (described in Attachment 2)
- 4. Discontinuation of study intervention due to lack of efficacy or an AE of worsening of UC
- 5. Discontinuation of study intervention due to COVID-19 related reasons (excluding COVID-19 infection) or regional crisis in Russia and Ukraine
- 6. Discontinuation of study intervention due to reasons other than those in ICEs 4 and 5

Estimand 3 (Alternative Mayo Calculation 1):

The attributes of this supplementary estimand are the same as those for the primary estimand with the exception of the Variable (Endpoint), where clinical remission at Week M-44 based on modified Mayo score components will be derived using an alternative calculation for the Mayo rectal bleeding subscore and stool frequency subscore instead of the methodology based on 3-day diary as detailed in Section 5.3.1. In this estimand, the Mayo rectal bleeding and stool frequency subscores will be calculated either based on eligible diary data (data not excluded from the calculation per Section 5.3.1.1.) collected on 3 consecutive days or, when 3 consecutive days are not available, all eligible diary data collected in a 7-day window prior to a clinical visit. If neither 3 consecutive days nor 4 nonconsecutive days are available, then the Mayo rectal bleeding and stool frequency subscores will not be calculated.

Estimand 4 (Alternative Mayo Calculation 2):

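### SAP 5.3.1.1 omits the protocol's diary-day exception for stable bulking or stool-softening agents, which can distort supplementary Estimands 3 and 7

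*SAP*

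**What the plan says.** Protocol 8.1.1 sets out which diary days may not be used for the stool frequency and rectal bleeding subscores. The first item is "The day on which medications for constipation, diarrhea, or irregularity were taken". The same item then makes an exception: for participants on a "stable dose of bulking or stool-softening agents throughout the study, the days on which these agents are taken should not be excluded". A later item makes a similar exception for chronic stable antimotility agents.

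SAP 5.3.1.1 restates the list. Its first bullet is "The day medications were taken for constipation, diarrhea or irregularity", with no exception attached. It does keep the antimotility exception, in a note that opens with "For participants maintained on a chronic stable dose of antimotility agents throughout the study, the days on which these agents are taken will not be" and goes on to retain those days for scoring. On the number of days, "Data from 3 of these 7 days are used to calculate the Mayo stool frequency and rectal bleeding subscores", and the sites tick those 3 days. "If 3 days (within the 7 days prior to the indicated visit) that meet the criteria defined above are not available", both subscores are missing.

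Estimand 3 (SAP 5.3.2.3) recalculates the subscores "based on eligible diary data (data not excluded from the calculation per Section 5.3.1.1"). Estimand 7 (SAP 5.4.2) does the same for four major secondary endpoints. It uses the same term, eligible diary data, without repeating the parenthetical reference. SAP Appendix 2 declares no changes to the analyses planned in the protocol.

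**The concern.** The rule that decides which diary days count should be the same in both documents, and it is not. Because the SAP carries one of the protocol's two exceptions forward, a programmer would reasonably take its list as complete.

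Estimands 3 and 7 ask whether the result depends on how diary days are chosen. If sites tick days under the protocol while these two estimands are programmed from the SAP list, stable users of bulking or stool-softening agents can be scored in the main analysis and unscorable in the supplementary one. Part of any gap between the two results would then come from the missing exception, and the comparison could no longer be read as a test of the diary method.

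**Working it through.** **1. The two lists side by side**

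- Days with medication for constipation, diarrhea or irregularity: excluded in both documents.
- Exception for stable bulking or stool-softening agents: in Protocol 8.1.1, absent from SAP 5.3.1.1. The SAP does not mention these agents anywhere.
- Exception for chronic stable antimotility agents: in both documents.

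The protocol writes the first exception under the medication item, which implies that these agents would otherwise fall under that exclusion.

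**2. Counting eligible days**

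Inputs: a 7-day window; at least 3 eligible days for the standard calculation (SAP 5.3.1.1); 3 consecutive or 4 nonconsecutive days for Estimands 3 and 7 (SAP 5.3.2.3 and 5.4.2). With u days of use and no other exclusion, eligible days = 7 − u under the SAP list.

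- u = 7: 7 − 7 = 0 days. Not scorable.
- u = 6 or 5: 1 or 2 days. Not scorable.
- u = 4: 3 days. Enough for the standard rule; enough for Estimands 3 and 7 only if the 3 days are consecutive.
- u = 3 or fewer: at least 4 days. Scorable under both.

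Under the protocol exception, a stable daily user keeps up to 7 days.

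**3. What a missing subscore does**

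SAP 5.3.2.3.1 applies nonresponder imputation to Estimands 2 to 5. For Estimand 7, SAP 5.4.2.1 carries over the rules of 5.4.1.3, which are also nonresponder imputation. A stable daily user is therefore a failure in both estimands, whatever the diary shows.

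**4. Size under Estimand 3**

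SAP Section 3 assumes 25% remission on placebo and 45% on guselkumab, with stated power of 90% at 118 per group and 97% at about 161 per group. A two-sided chi-square calculation at 0.05 gives 90.1% and 96.7%, so the plan's figures reproduce. They are not in dispute; only the rates and group size are used here.

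The documents give no share of stable daily users. Let the share be f, assumed equal across arms and unrelated to outcome. Each Estimand 3 rate becomes p × (1 − f), with 161 × f participants per group affected.

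- f = 1%: 161 × 0.01 = 1.6 per group; 24.75% vs 44.55%; difference 19.8 points.
- f = 5%: 161 × 0.05 = 8.1 per group; 23.75% vs 42.75%; difference 19.0 points.
- f = 10%: 161 × 0.10 = 16.1 per group; 22.5% vs 40.5%; difference 18.0 points.

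At f = 5% the guselkumab rate under Estimand 3 would sit 45 − 42.75 = 2.25 points below the main result with no difference in disease. These figures describe Estimand 3 read literally, not the primary analysis.

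**The case against.** The strongest reply is that the SAP list is a shortened account of site instructions, not a new rule. SAP 5.3.1.1 cites Protocol 8.1.1 for the Mayo score, describes what sites are directed to do, and has sites tick the days. Appendix 2 says nothing was changed. Sites work under the protocol, which keeps these days. For the main analysis this reply stands.

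A reader might infer that stable users become automatic non-remitters on the primary endpoint and that primary power falls. The documents do not support that. It would require sites to have received the SAP wording in place of the protocol's, and the eCRF completion instructions that would settle it are not among the documents. A reader might also extend the point to flare, loss of response and the 12-week partial Mayo decision. Those are made at the site under Protocol 4.1.3.1 with scores defined in Protocol 8.1.1, so the SAP wording does not govern them.

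Other limits also stand:

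- Estimands 4 and 8 use all available diary days except the endoscopy day and the day before, so the list does not touch them.
- Protocol 6.5 discourages laxatives outside preparation for procedures, which points to few users.
- Estimands 3 and 7 are supplementary and outside the Type I error procedure.
- The SAP does not say whether eligibility for Estimand 3 comes from site entries or from programmed matching to medication records.

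The last point leaves open how the list would be applied. It does not change the fact that Estimand 3 names Section 5.3.1.1 as its definition of eligible data.

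**Conclusion.** The omission is certain: the SAP lacks an exception that the protocol contains, and it is not declared as a change. Followed as written, the SAP makes a stable daily user unscorable, and so a nonresponder, under Estimand 3 and, by the same term, Estimand 7.

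The size is unknown and probably small. The 1% to 10% range is an assumption; within it the Estimand 3 difference falls from 20.0 to between 19.8 and 18.0 points. The conclusion rests on three premises: that these agents count as medication for constipation, diarrhea or irregularity; that Estimand 3 is programmed from the SAP list; and that the affected participants use the agents on most days. The main analysis is unaffected if sites applied the protocol rule, and no loss of primary power is claimed. What is at stake is whether two supplementary analyses can be interpreted.

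**What to change.** Under the first exclusion bullet in SAP 5.3.1.1, add the Protocol 8.1.1 exception: for participants on a stable dose of bulking or stool-softening agents throughout the study, days of use are kept. State in SAP 5.3.2.3 and 5.4.2 that this completed list defines eligible diary data for Estimands 3 and 7. Check that the eCRF completion instructions given to sites carry the same exception. If the omission was intended, declare it in Appendix 2 with the reason.

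The cost is a sentence or two in the SAP before the Week M-44 database lock. It needs no new data and brings the SAP back to the protocol's existing rule.

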5.3.2. Primary Estimand (Estimand 1)

The primary estimand, i.e., a precise definition of the primary targeted treatment effect is defined by the following 5 attributes:

Randomized Maintenance Treatment by Week M-44:

Experimental:

- Guselkumab 200 mg SC q4w
- Guselkumab 100 mg SC q8w

Control:

• Placebo SC

Population: Patients 18 years or older with moderately to severely active UC as reflected in the inclusion/exclusion criteria (Protocol Section 5) along with a requirement of a modified Mayo score of 5 to 9 who were induced into clinical response with guselkumab.

Variable: Clinical remission at Week M-44 (Section 5.3.1.) where participants are considered to have achieved clinical remission if they fulfill the clinical remission criteria based on modified Mayo score components (Section 5.3.1.1.), and do not experience intercurrent events in categories 1-4 and 6 (defined below) prior to the Week M-44 visit.

Intercurrent Events and Corresponding Strategies:

The following are the intercurrent events for this study:

- 1. An ostomy or colectomy (partial or total)
- 2. Have a dose adjustment (including a sham dose adjustment; Section 1.3.1)
- 3. Prohibited change in UC medication (described in Attachment 2)
- 4. Discontinuation of study intervention due to lack of efficacy or an AE of worsening of UC
- 5. Discontinuation of study intervention due to major disruption, including COVID-19 related reasons (excluding COVID-19 infection) or regional crisis in Russia and Ukraine
- 6. Discontinuation of study intervention due to reasons other than those in ICEs 4 and 5

Intercurrent events (ICEs) in categories 1-4 and 6 will be handled with the composite strategy as reflected in the variable definition. ICE category 5 will be handled by the Treatment Policy Strategy. Note that the application of ICE categories 1-3 overrides that of ICE 5. This means that a participant with ICE in categories 1-3 will be considered as not to have achieved the variable, regardless of whether the participant has had an ICE 5. For participants experiencing ICE 5, their observed clinical remission status (if available) at Week M-44 will be used.

Population-level summary:

The difference in the proportion of participants achieving the variable (as defined above for this estimand) between each guselkumab group and the placebo group.

Note: This estimand acknowledges that having an intercurrent event in categories 1-4 and 6 is an unfavorable outcome.

5.3.2.1. Analysis Methods

5.3.2.1.1. Main Estimator (Analysis) for the Primary Estimand

The primary endpoint is clinical remission at Week M-44 (as defined in Section 5.3.1. above).

The primary endpoint will be analyzed based on the Primary Estimand, Estimand 1 (Section 5.3.2.). After accounting for the ICE strategies, participants who are missing any or all of the Mayo subscores that comprise the primary endpoint at Week M-44 will be considered not to be in clinical remission at Week M-44 (i.e., nonresponder imputation). For participants experiencing ICE 5, their observed clinical remission status (if available) at Week M-44 will be used.

In the primary analysis, data from all participants in the **Randomized Full Analysis Set** (Section 4) will be analyzed according to the randomized study intervention regardless of the study intervention they actually received.

Summaries of the proportion of participants in clinical remission at Week M-44 (as well as the associated 95% confidence interval) by treatment group, the adjusted treatment difference (with Cochran-Mantel-Haenszel weight) between each guselkumab treatment group and the placebo group, as well as the associated 95% confidence interval will be presented.

For testing of the primary endpoint, the efficacy of each guselkumab group versus placebo will be compared. For all statistical comparisons of the primary endpoint, a Cochran-Mantel-Haenszel (CMH) test (2-sided) stratified by clinical remission status at maintenance baseline (Yes/No), and induction dose treatment (guselkumab 400 mg, guselkumab 200 mg, placebo crossover to guselkumab 200 mg) will be used.

A multiplicity-controlled testing procedure, starting with the high guselkumab dose group (200 mg SC q4w), will be used to control the overall Type-I error rate at the 0.05 level (2-sided) over the primary and major secondary endpoints. The study will be considered positive if the test involving

the high maintenance dose group shows a statistically significant difference versus placebo for the primary endpoint of clinical remission at Week M-44 (see Section 5.4.1.3).

Testing Procedure:

The multiple testing procedure to control the Type 1 error will be different for the United States and the countries outside the United States, as described below.

Type I error control for Rest of World (i.e., countries outside the United States): A fixedsequence testing procedure will be used to control the overall Type I error rate at the 0.05 level for the primary endpoint. Specifically, the high maintenance dose group (200 mg SC q4w) will be considered significant if its p-value vs placebo is < 0.05. The low maintenance dose group (100 mg q8w) will be significant if the p-value vs placebo for both high and low maintenance dose groups are < 0.05.

Type I error control in the United States (US-specific testing procedure): A fixed-sequence testing procedure will be employed for the United States to strongly control the overall Type 1 error rate at the 0.05 level across the primary and all the major secondary endpoints (except for IBDQ remission, which is not considered a major secondary endpoint in the US-specific testing procedure) and across the 2 guselkumab doses, starting with the high maintenance dose group (200 mg SC q4w) of the primary endpoint. The exact testing procedure is detailed in Section 5.4.1.3.

